It is expected that treatment with evinacumab will be well tolerated and have an acceptable safety profile. The accumulated safety information from the completed and ongoing clinical studies is marked by the absence of any important identified risks. There are potential risks that include systemic hypersensitivity reactions, immunogenicity, and embryofetal toxicity. These risks will be

managed through careful patient selection and monitoring. For the potential embryofetal toxicity risk, there is a strict risk mitigation plan, including requirements for consistent use of contraception for sexually active male study participants and sexually active female study participants of child bearing potential.

Taken together, these data show the positive benefit/risk assessment of treatment with evinacumab in patients with HeFH, or non-HeFH with clinical ASCVD with persistent hypercholesterolemia despite receiving maximally-tolerated LMT. Persistent hypercholesterolemia is defined as LDL-C ≥ 70 mg/dL (1.81 mmol/L) for those patients with clinical ASCVD and LDL-C ≥ 100 mg/dL (2.59 mmol/L) for those patients without clinical ASCVD.

To obtain long-term safety data with evinacumab, all patients in Group B will receive IV study drug for 48 weeks. Due to the injection burden of weekly SC administration, Group A patients will not be required to receive study drug for 48 weeks. After the 16-week double-blind treatment period, Group A patients who wish to receive treatment with evinacumab may have the opportunity to enroll in an open-label extension or safety study. Therefore, this study design took into consideration the objective of obtaining long-term safety data and providing potential benefit to patients with continued treatment with evinacumab while balancing the burden of frequent study visits and SC injections.

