 - Investigator or any sub-investigator, pharmacist, study coordinator, other study staff or relative thereof directly involved in the conduct of the protocol, etc.
 - Presence of any other conditions (eg, geographic or social), either actual or anticipated, that the investigator feels would restrict or limit the patient's participation for the duration of the study
12. Laboratory findings during screening period (not including randomization labs):
- Triglycerides >400 mg/dL (>4.52 mmol/L) for patients without a known history of diabetes mellitus (1 repeat lab is allowed);
OR
Triglycerides >300 mg/dL (>3.39 mmol/L) for patients with a known history of diabetes mellitus (1 repeat lab is allowed)
 - Positive test for Hepatitis B surface antigen and/or Hepatitis C antibody (associated with a positive HCV ribonucleic acid [RNA] polymerase chain reaction)
 - Positive serum beta-human chorionic gonadotropin or urine pregnancy test in women of childbearing potential
 - Estimated glomerular filtration rate <30 mL/min/1.73 m² according to 4-variable MDRD study equation (calculated by central lab)
 - TSH >1.5 x upper limit of normal (ULN) (1 repeat lab is allowed) for patients not on thyroid replacement therapy
 - Alanine aminotransferase (ALT) or aspartate aminotransferase (AST) > 2 x ULN at screening (1 repeat lab is allowed)
 - Creatine phosphokinase (CPK) > 3 x ULN at screening (1 repeat lab is allowed)
13. Systolic blood pressure > 160 mmHg or diastolic blood pressure > 100 mmHg at the screening visit or time of randomization (1 repeat allowed)
14. History of heart failure (New York Heart Association [NYHA] Class III-IV) within 12 months before screening

15. History of MI, unstable angina leading to hospitalization, CABG surgery, PCI, uncontrolled cardiac arrhythmia, carotid surgery or stenting, stroke, TIA, carotid revascularization, endovascular procedure or surgical intervention for peripheral vascular disease within 3 months prior screening
16. Having received LDL apheresis within 2 months before screening
17. Evidence of clinically significant intestinal malabsorption, or a history of ileal bypass, gastric bypass, or other bariatric surgery within 12 months before screening
18. Unstable weight (variation > 5 kg) within 2 months prior to screening visit

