19. Significant concomitant illness including, but not limited to: cardiac, renal, neurological, endocrinological, hepatic, metabolic, or lymphatic disease, that would adversely affect the patient's participation in the study
20. History of cancer within the past 5 years, except for adequately treated basal cell skin cancer, squamous cell skin cancer, or in situ cervical cancer
21. Known hypersensitivity to monoclonal antibody therapeutics
22. History of a hypersensitivity reaction to PCSK9 inhibitor antibodies
23. Participation in a clinical research study evaluating an investigational drug within 30 days, or at least 5 half-lives of the investigational drug, before screening, whichever is longer
24. History or evidence of drug or alcohol abuse within 12 months before screening
25. History of noncompliance to medical treatments
26. Pregnant or breast-feeding women
27. Women of childbearing potential* who are unwilling to practice a highly effective birth control method prior to the initial dose, during the study, and for 24 weeks after the last administration of study drug. Highly effective contraception measures include:
 - Stable use of combined (estrogen and progestogen containing) hormonal contraception associated with inhibition of ovulation initiated 2 or more menstrual cycles prior to screening:
 - oral
 - intravaginal
 - transdermal
 - Stable use of progestogen-only hormonal contraception associated with inhibition of ovulation initiated 2 or more menstrual cycles prior to screening:
 - oral
 - injectable
 - implantable
 - Intrauterine device
 - Intrauterine hormone-releasing system

- Bilateral tubal ligation
- Vasectomized partner. Note: Vasectomized partner is a highly effective birth control method provided that the partner is the sole sexual partner of the WOCBP study participant and that the vasectomized partner has received medical assessment of the surgical success.
- Sexual abstinence. Note: Sexual abstinence is considered a highly effective method only if defined as refraining from heterosexual intercourse during the entire period of risk associated with study treatments.

True abstinence: When this is in line with the preferred and usual lifestyle of the patient. Periodic abstinence (calendar, symptothermal, post-ovulation methods), withdrawal (coitus interruptus), spermicides only, and lactational amenorrhea method (LAM) are not acceptable methods of contraception

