*Postmenopausal women must be amenorrheic for at least 12 months in order not to be considered of childbearing potential. Postmenopausal status will be confirmed by measurement of follicle-stimulating hormone (FSH). Pregnancy testing and contraception are not required for women with documented hysterectomy and/or oophorectomy.

Oocyte donation is prohibited during the study and for 24 weeks after the last administration of study drug.

28. Men who are sexually active with WOCBP and are unwilling to consistently use condoms during the study drug treatment period and for 24 weeks after the last administration of study drug, regardless of vasectomy status. Sperm donation is prohibited during the study and for up to 24 weeks after the last administration of study drug.

29. Member of the clinical site study team and/or his/her immediate family.

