7.4.2.1. Reasons for Permanent Discontinuation of Study Drug

Study drug dosing will be permanently stopped in a patient in the event of the following, but not limited to:

- Evidence of pregnancy
- Acute systemic injection/infusion reactions with AEs including, but not limited to, anaphylaxis, laryngeal/pharyngeal edema, severe bronchospasm, chest pain, seizure, or severe hypotension
- Patient requires a prohibited concomitant medication during the study. The principal investigator should contact the Regeneron study monitor. Based on the discussion, study drug may be continued, or may be temporarily or permanently discontinued
- Patient withdraws consent

The investigator may permanently discontinue dosing with study drug at any time, even without consultation with the medical monitor, if the urgency of the situation requires immediate action and if this is determined to be in the patient's best interest. However, the medical monitor should be contacted as soon as possible in any case of permanent study drug discontinuation.

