8.1.1. Footnotes for the Schedule of Events Tables

EOS = end of study; EOT = end of treatment; U = urine; Core lipid panel = TC, calculated LDL-C, HDL-C, TGs, and non-HDL-C; Specialty lipid panel = ApoB, ApoA-1, ratio ApoB/ApoA-1, and Lp(a).

1. All patients will be reminded of protocol-specified contraception use and pregnancy reporting.
2. All laboratory samples should be collected before the administration of study drug. All samples should be collected following at least an 8-hour fast.
3. Electrocardiograms should be performed before blood is drawn during visits requiring blood draws.
4. On dosing days, PK collection should occur pre-dose for group A and prior to IV infusion and at the end of the IV infusion for group B.
5. LDL-R function samples will be collected from a sub-set of patients based on enrollment and will be determined by IWRS.

- [REDACTED]
- [REDACTED]
- [REDACTED]
7. For SC dosing, patients will be observed at the clinical site for at least 30 minutes following each SC study drug administration. For IV dosing, patients will be monitored for at least 60 minutes following the end of each IV study drug administration.
 8. Starting at W1 and every odd visit week (ie, W3, W5, W7, etc) thereafter, visiting home nurses may administer study drug for those patients randomized to Group A.
 9. WOCBP will be provided urine pregnancy tests with instructions to test for pregnancy at home.
 10. All subjects will be contacted by phone to query LMT compliance, inquire about AEs or changes to concomitant medications, confirm required contraception use and remind patients of pregnancy reporting. Women of childbearing potential will report the results of their home urine pregnancy test. All patients will also be queried regarding their low fat diet.
 11. Vital signs should be recorded prior to SC injection or IV infusion, and 30 minutes and 60 minutes post-IV infusion.

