8.2.3.5. Pregnancy Testing

Women of childbearing potential will undergo pregnancy testing approximately every 4 weeks throughout the study from baseline through EOS. Pregnancy testing will be via a urine pregnancy test, except for the screening visit and EOS visit, which will be via a serum pregnancy test. During some follow-up visits, and in case of early termination, pregnancy testing may occur at home via a urine pregnancy test where the results will be reported to the clinical site by the patient.

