9.4.3. Other Events that Require Accelerated Reporting to Sponsor

The following events also require reporting to the sponsor (or designee) within 24 hours of learning of the event:

Symptomatic Overdose of Study Drug: Accidental or intentional overdose of at least 2 times the intended dose of study drug within the intended therapeutic window, if associated with an AE

Pregnancy: Although pregnancy is not considered an AE, it is the responsibility of the investigator to report to the sponsor (or designee), within 24 hours of identification,

any pregnancy occurring in a female or female partner of a male, during the study or within 24 weeks of the last dose of study drug. Any complication of pregnancy affecting a female study patient or female partner of a male study patient, and/or fetus and/or newborn that meets the SAE criteria must be reported as an SAE. Outcome for all pregnancies should be reported to the sponsor

Adverse Events of Special Interest: All AESIs, serious and non-serious, must be reported within 24 hours of identification using the same reporting process as for SAE reporting, per Section 9.4.2.

Adverse events of special interest for evinacumab include the following:

- Anaphylactic reactions
- Allergic reactions and/or local injection site reactions that require medical treatment or consultation with another physician for further evaluation
- Increase in ALT or AST: ≥ 3 x ULN (if baseline < ULN), or ≥ 2 x baseline value (if baseline \geq ULN)
- Pregnancy
- Symptomatic overdose with IMP
- Neurocognitive events
- New onset of diabetes
- Pancreatitis

Adverse events of special interest for alirocumab include the following:

- Increase in ALT: ALT ≥ 3 x ULN (if baseline ALT < ULN), or ALT ≥ 2 x baseline value (if baseline ALT \geq ULN)
- Allergic events and/or local injection site reactions that require consultation with another physician for further evaluation
- Pregnancy
- Symptomatic overdose with IMP
- Neurologic events that require additional examinations/procedures and/or referral to a specialist
- Neurocognitive events
- Cataracts
- New onset of diabetes:

The definition of new onset of diabetes will be the following:

- Type 1 or type 2 diabetes treatment-emergent adverse event (TEAE) (grouping of MedDRA terms will be specified in the SAP)

and/or

- at least 2 values of HbA1c $\geq 6.5\%$ during the TEAE period

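### The surgical waiver under exclusion criterion 27 does not require both ovaries to be removed, so read literally it exempts a fertile woman from pregnancy testing and contraception

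*Protocol*

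**What the plan says.** Criterion 27 excludes women of childbearing potential who will not use highly effective birth control before the first dose, during the study and for 24 weeks after the last dose. An asterisked note describes who falls outside the requirement. Postmenopausal women do so after at least 12 months of amenorrhea, with FSH confirmation. The note then adds a surgical waiver: "Pregnancy testing and contraception are not required for women with documented hysterectomy and/or oophorectomy".

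The list of accepted methods in the same criterion does state laterality where it matters: "Bilateral tubal ligation".

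Protocol Section 8.2.3.5 sets the testing rule that the waiver switches off: "Women of childbearing potential will undergo pregnancy testing approximately every 4 weeks throughout the study from baseline through EOS". Section 3.2.3 gives the reason for these rules: "For the potential embryofetal toxicity risk, there is a strict risk mitigation plan, including requirements for consistent use of contraception".

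**The concern.** The waiver joins the two operations with and/or, so either one is enough, and it attaches no laterality to oophorectomy. A woman who has lost one ovary has a documented oophorectomy. If she is premenopausal and has a uterus, she can conceive, yet the note says that neither testing nor contraception is required of her.

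What is at stake is fetal exposure to a drug whose potential embryofetal toxicity the protocol sets out to manage. Women from age 18 are eligible, so premenopausal women can enrol. Group B dosing covers 24 weeks double-blind plus 48 weeks open-label, 72 weeks in all. About 80 sites will apply the text, and a site that follows it literally commits no deviation that monitoring would pick up.

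**Working it through.** There is no sponsor figure to reproduce. The check has two parts: whether any other text closes the gap, and how much protection the literal reading removes for one woman.

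**Does any other text close the gap?**

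- *Rest of the note to criterion 27.* The postmenopausal sentences are a separate route and do not limit the surgical one.
- *Criterion 12, screening laboratory findings.* It excludes for "Positive serum beta-human chorionic gonadotropin or urine pregnancy test in women of childbearing potential". It applies to women of childbearing potential, from whom the note has just lifted the test.
- *Criterion 26.* It excludes pregnant women, but acts only if the pregnancy is known.
- *Section 7.4.2.1.* The stopping rule is "Evidence of pregnancy". It also depends on the pregnancy being detected.
- *Section 8.1.1, footnote 1.* "All patients will be reminded of protocol-specified contraception use and pregnancy reporting". For an exempt woman the protocol specifies no contraception, so the reminder restores nothing.
- *Section 9.4.3.* It requires 24-hour reporting of "any pregnancy occurring in a female or female partner of a male, during the study or within 24 weeks of the last dose". This acts after the event.
- *SAP.* It neither defines childbearing potential nor limits oophorectomy.

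Nothing supplies the missing limit.

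**What is waived for one woman, at most?** The counts come from the pregnancy-test and dosing rows of Protocol Tables 1 to 7 and include home tests during follow-up.

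| Item | Count | Total |
|---|---|---|
| Group B tests | screening 1 + weeks 0–48 every 4 weeks 13 + weeks 52–72 6 + weeks 76–92 5 | 25 |
| Group B, with run-in pre-screening urine test | 25 + 1 | 26 |
| Group B, entering the separate open-label study after week 72 without follow-up | 25 − 5 | 20 (21 with run-in) |
| Group B infusion visits, each with a scheduled test | double-blind weeks 0–20 6 + open-label weeks 24–68 12 | 18 |
| Group A tests | screening 1 + weeks 0, 4, 8, 12, 16 5 + weeks 20, 24, 28, 32, 36, 39 6 | 12 |
| Group A, with run-in | 12 + 1 | 13 |

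The reduction to 20 applies only in Group B. Section 5.1.2 lets Group B patients join the open-label study straight after treatment, whereas Group A patients must complete follow-up first.

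The contraception requirement runs 24 weeks past the last dose:

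- Group B: week 68 + 24 = week 92.
- Group A: week 15 + 24 = week 39.

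**The case against.** The best reply is that the note never reclassifies this woman. The postmenopausal sentence says who is no longer considered of childbearing potential. The surgical sentence says only that testing and contraception are not required. In plain meaning she still has childbearing potential, so criterion 12, criterion 27 itself and Section 8.2.3.5 would still cover her. That is a fair reading, but it gives two conflicting instructions, and a specific waiver would normally prevail over a general rule.

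Context also points to both ovaries. The sentence follows the postmenopausal rule and pairs oophorectomy with hysterectomy, and the tubal ligation entry shows that the drafters knew one-sided surgery is not enough. The operation must be documented, so a site has a record to check, and an investigator would have to overlook a working ovary for harm to follow. I accept that this is probably what was meant and that many sites would read it so. It is a reason to write the word.

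There are further safeguards. Sexually active patients are reminded at the end of treatment to continue contraception for 24 weeks (Section 5.1.2), and again after early discontinuation, when all patients are told of 4-weekly calls to confirm contraception use (Sections 6.3 and 8.1.2). An investigator may also test without being required to, or exclude a patient as unsuitable under criterion 11. These make a silent lapse less likely, but none is a scheduled test or a contraception requirement.

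Finally, the visit counts describe one hypothetical woman and do not estimate pregnancies. That is correct, and they should be read only as the extent of the waiver.

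**Conclusion.** The concern holds. As written, the waiver exempts a premenopausal woman with a uterus and one ovary, and no other text in either document limits it. Under that literal reading she loses up to 25 scheduled tests in Group B (26 with a run-in) or 12 in Group A (13 with a run-in), together with the contraception requirement. The safeguards that remain are reminders or act only once a pregnancy is known.

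This conclusion rests on a site following the words as they stand. The documents do not give the number of women with a single oophorectomy, and it is probably small. The issue is patient safety alone, with no bearing on sample size, power, type I error or the efficacy analysis. The sponsor should correct it.

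**What to change.** In the note to criterion 27, insert *bilateral* before *oophorectomy*, so that the exempting surgery reads *hysterectomy and/or bilateral oophorectomy*. Leave the hysterectomy exemption and the postmenopausal sentences as they are.

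The change is one word. Its only downside is that a few more women are tested and counselled on contraception.

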6.3. Premature Withdrawal from the Study

A patient has the right to withdraw from the study at any time, for any reason, and without repercussion.

The investigator and/or sponsor have the right to withdraw a patient from the study if it is no longer in the interest of the patient to continue in the study, or if the patient's continuation in the study places the scientific outcome of the study at risk (eg, if a patient does not or cannot follow study procedures). An excessive rate of withdrawals would render the study uninterpretable; therefore, unnecessary withdrawal of patients should be avoided.

Patients who are withdrawn prematurely from the study will be asked to complete study assessments, as described in Section 8.1.2.

Rules for discontinuation of study drug (permanent or temporary) are discussed in Section 7.4.2.

Early Termination from the Study

If for any reason the patient refuses to continue the study, the patient should undergo an unscheduled visit with assessments normally planned at the EOT visit (it should take place within 5 days of treatment discontinuation, if possible).

For patients that discontinue the study prematurely, the patient should be followed for at least 24 weeks from the last dose of study drug or up to recovery or stabilization of any AE to be followed-up as specified in this protocol, whichever comes last. A final EOS visit should take place with assessments as specified in the EOS visit (ie, follow-up visit) at 24 weeks after the last dose of study drug.

Sexually active patients who discontinue the study prematurely should be reminded at the unscheduled visit following treatment discontinuation to maintain highly effective contraceptive measures for 24 weeks after the last dose of study drug. At this visit, WOCBP will be provided 5 urine pregnancy tests with instructions to test for pregnancy 4 weeks after this visit and Q4W thereafter. All patients should also be notified of Q4W follow-up phone calls to confirm contraception use, remind them of pregnancy reporting, and to obtain the results of the urine pregnancy test.

The investigator or study staff should make the best effort to contact any patient (eg, contacting patient's family or private physician, review available registries or health care database) who fails to return to the site, and to determine health status, including at least vital status. Attempts to contact such patients must be documented in the patient's records (eg, times and dates of attempted telephone contact, receipt for sending a registered letter). The site will be provided a retention manual outlining the best practices for patient retention.

6.4. Replacement of Patients

Patients who prematurely discontinue from the study will not be replaced.

7. STUDY TREATMENTS

7.1. Investigational Treatments and Reference Treatments

Evinacumab or placebo will be supplied for SC or IV administration. Study treatment groups are defined in Section 5.1.1.

For patients who are not receiving a PCSK9 inhibitor antibody, sterile alirocumab drug product will be supplied at a concentration of 150 mg/mL in a prefilled pen.

All SC injections will be administered in the abdomen, thigh, or outer area of the upper arm with rotating sites of injection. Instructions for management of acute injection site and infusion reactions are provided in Section 7.5.

For SC QW regimen the dose should be administered ± 3 days; if ≥ 4 days have passed, skip the dose and return to the original schedule. For IV Q4W regimen the dose should be administered ± 14 days; if >14 days have passed, skip the dose and return to the original schedule.

The IV dose should be prepared using the patient's most recent weight. Further instructions on dose preparation are provided in the pharmacy manual.

